Phase I: To create VR-M to focus on virtual reality job interview training for transition-age youth with ASD receiving vocational services. We will solicit feedback on the training tool using mixedmethod semi-structured feedback forms with high school (HS) youth with ASD (n=20) or other educationally defined disabilities (n=10) as well as employed adults with ASD or other prior educational disability as well as parents, employers, and vocational counselors that support youth with ASD, educational disability, or adjudication (n=30) to systematically evaluate the core components of VR (e.g., interview content, virtual character, VR interface, and didactic content). Qualitative interview data will be analyzed for themes regarding technical content-based limitations of VR. SIMmersion will then integrate the qualitative results to create a tailored learning system.

Phase II: To evaluate the feasibility and preliminary effectiveness of VR-M in a randomized pilot trial comparing vocational-services-as-usual with VR-M added on (VSU+VR-M) to VSU only. Transition-age youth with ASD (n=90) will be enrolled in a 6-month trial to test all study protocol

3 of 24

aspects including VR-M training effectiveness, recruitment procedures, and assessment tools. VR-M will be administered at educational programs supporting rural, suburban, and urban youth to capture greater variation in programming and students. We will monitor VR-M treatment fidelity, acceptability, usability, feasibility, and tolerability.

Phase IIa: To assess whether VR-M is associated with enhanced job interview skills (primary target) and interviewing self-confidence, and reduced interviewing anxiety. Compared to VSU, the VSU+VR-M group will improve interview skills (Hyp 1), increase self-confidence (Hyp 2), increase motivation (Hyp 3) and reduce anxiety (Hyp 4).

Phase IIb: To assess whether VR-M is associated with higher employment rates and attaining employment sooner at 6-month follow-up. Compared to VSU, the VSU+VR-M group will: a) have a greater likelihood of attaining employment (Hyp 5) and b) attain employment sooner at 6-month follow-up (Hyp 6).

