Exploratory Aim 1: To develop hypotheses for future trials, we will explore mechanisms for improving interview skills and employment outcomes (mediators) or differential response to VR-M (moderators) as well as conduct a preliminary evaluation of VR-M delivery within a school setting. Mediators will include interview skills (for evaluating outcomes), self-confidence, and anxiety. Moderators will include VR-M performance scores and ASD heterogeneity variables (i.e., ASD-symptoms (e.g., social communication), depressive symptoms, and cognition). We will also explore ASD heterogeneity as a mechanism for differential response to VR-M, and collect exploratory implementation data.

Pilot Implementation Aim: To conduct a preliminary implementation evaluation of delivering the new VR-M to students in educational programming. We will ask teachers (n= 30) to complete Installation Cost Capture forms, Delivery Cost Capture forms, Teacher Context Form and a brief survey regarding their use of evidence based practice and whether they observed any factors that became barriers to delivering VR-M or factors that helped facilitate the delivery and feasibility of VR-M. Teachers may also be asked to participate in an audio recorded semi-structured interview. We will provide up to \$45.00 in gift cards for participation in total.

2.0 Background / Literature Review / Rationale for the study:

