about why a response was helpful for hurtful to their job interview and learn how Travis/Rita understood their responses.

C.1.i. Scoring and Summary Feedback: After each virtual interview, trainees receive scores in categories based on the learning goals. The scores are scaled form 0-100 and are computed via an algorithm, which accounts for the types of responses provided by the trainee throughout the course of the interview. Participants view this scoring feedback and if they score 80 or higher they are informed if they got the job or not. Trainees also receive feedback summaries of what they did well and where they need improvement. This feedback helps trainees understand the subtleties of their interview skills.

D. Study Visit Procedures

The research team will evaluate the initial effectiveness of the training by conducting a randomized controlled trial (RCT) at Ann Arbor Academy and Troy Beaumont Hospital Project Search.

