The PI and or study team will be available to answer any questions the parents may have while reviewing the permission form. After the parents return the form, students under 18 years of age will be approached at school during Study Visit 1 to provide assent. Parents and students will be informed that choosing not to participate will not affect their or the student's relationship with the school or teachers. For students 18 years or older, the research team will send an informational letter home informing the parents of the study and then the research team will approach the students 18-26 years old in order to obtain written informed consent.

Also, teachers from all schools/programs will be recruited to participate in this study as part of an initial implementation. The teachers will be recruited beforehand during a phone call, or through the same educational meeting hosted at the school to inform parents and recruit students.

D.1. Pre-Study Visit:

Parents and teachers will be asked to complete surveys prior to Study Visit 1. Surveys will be administered electronically, or by pen and paper. Completers will receive \$15 (parents and/or teachers).

Parents will be asked to complete:

- 1. Student Background Form and Contact Info Form (age, gender, race, ethnicity, etc.)
- 2. Behavior Checklist (ABCL or CBCL) (Achenbrock & Edelbrock, 2001). These surveys assess behavioral problems and social competencies as reported by parents and/or teachers. They are standardized in the field and have a long history of validity and reliability. If parents do not complete this form, then we will ask the teachers to do so (ABCL/CBCL/TRF).
- 3. Social Responsiveness Scale 2nd Edition (SRS-2) (Constantine & Gruber, 2005), which is a teacher/parent based rating scale that measures the severity of autism spectrum symptoms

Teachers will be asked to complete:

- 1. Teacher Demographic Form
- 2. Social Responsiveness Scale 2nd Edition (SRS-2) (Constantine & Gruber, 2005), which is a teacher/parent based rating scale that measures the severity of autism spectrum symptoms
- 3. Behavior Checklist (ABCL/CBCL/TRF) if parents do not complete the form
- 4. Student Background Form and Contact Info if parents do not complete the form

D.2. Study Visit 1 & 2:

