These visits should last approximately 60 minutes each. Students will receive a \$25 gift card for each visit. The consent and reading test will always be first, but the following activities may be done in a different order depending on the student availability. We aim to work best within the school and their availability. Study staff will complete the following tasks with student:

- Assent/Consent
- Reading Level: Wide Range Achievement Test (4th Edition) to assess current reading level. (If students do not pass a 3rd grade reading level, participation will end and they will be compensated \$10).
- Cognitive Assessments on an iPad using the National Institute of Health Tool Box
 Application
- Baseline Employment Survey
- Mood Survey
- Job practice interview Role-Play (audio and video recorded)
- Self-Report Surveys about:
 - a. Anxiety
 - b. Motivation
 - c. Self-confidence

D.4. Randomization:

Students will be randomized into the VR-M group or the control group. This will be done at a ratio of 2:1 (VR-M:control). Family and teachers will be informed by research team if student is active in the Intervention group or the Control group. The Control group will continue their educational services as usual and skip "visits" 3-16. They will return for the last in person Study Visit 17. Block randomization

tables will be created prior to the study based on computer generated blocks of four. Blocks of four will ensure nearly equal groups. Envelopes or paper containing the randomization by sequential subject entry number will be created and stored, and then opened when a participant has completed pre-randomization procedures.

D.5. Study Visit 3:

Students randomized to the VR-M group will receive a 45-60 minute orientation to use the Virtual Interview Training program.

D.6. Study Visit 4:

Students will train with the educational content. Study staff will be on site to help troubleshoot and answer questions if needed.

D.7. Study Visit 5:

Students will use one class period for orientation to learn to navigate and participant in the virtual interview.

D.8. Study Visit 6-16:

Students will complete up to 3 virtual job interviews per class period. Teachers will help implement this in their classrooms and may decide to utilize homework for the students where they are assigned to use the tool at home as well as in the school.

D.9. Study Visit 17:

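### VR-M performance scores cannot moderate the VR-M effect: they arise after randomisation and exist only in the VR-M arm

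*Combined protocol and SAP*

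**What the plan says.** Section 1.0, Exploratory Aim 1, sets out to explore mediators and "differential response to VR-M (moderators"). It then states "Moderators will include VR-M performance scores and ASD heterogeneity variables", the latter being ASD symptoms, depressive symptoms and cognition. The aim is to generate hypotheses for later trials.

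The source and timing of the scores are in Section 4.0:

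- C.1.i: "After each virtual interview, trainees receive scores in categories based on the learning goals". They run from 0 to 100 and come from the software.
- D.4: allocation is 2:1. "The Control group will continue their educational services as usual and skip" visits 3 to 16.
- D.8, covering visits 6 to 16: "Students will complete up to 3 virtual job interviews per class period".

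The other listed moderators are measured before randomisation in all students. D.1 has the SRS-2, "which is a teacher/parent based rating scale that measures the severity of autism spectrum symptoms". D.2 has the mood survey and "Cognitive Assessments on an iPad using the National Institute of Health Tool Box".

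Section 14.0 names linear regression as the method for moderators. It gives no arm-by-moderator term for any of them and no separate handling for the VR-M scores. Its own lists of moderators are given as examples and do not mention the scores.

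**The concern.** A variable moderates the effect of VR-M if the difference between VSU+VR-M and VSU changes with its value. Estimating that requires the variable in both arms, and it should not itself be a product of treatment. The VR-M score fails on both counts.

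Only an association between score and outcome among VR-M students can be computed. It mixes prior ability, amount of practice and whatever the training did. Reported under the moderator heading, it could be read as identifying who benefits from VR-M. Since the aim exists to guide later trials, the risk is that a later trial selects or targets students on a signal that this design cannot provide.

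**Working it through.** The documents give no power calculation or effect size for this analysis, so there is no stated figure to reproduce. The check is whether the model can be estimated and, if not, what the remaining analysis shows.

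**Inputs from the documents.** Total size: "Transition-age youth with ASD (n=90) will be enrolled in a 6-month trial" (Section 1.0, Phase II). At 2:1 this is 90 × 2/3 = 60 VR-M and 30 control students. Scores exist only for the 60.

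**1. Estimability.** Take outcome = b0 + b1·arm + b2·score + b3·(arm × score).

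- *Controls left missing.* Complete cases are 60 VR-M students and 0 controls. Then arm equals the intercept and arm × score equals score, giving rank 2 of 4. With pretest added, the rank is 3 of 5.
- *Controls given a constant c.* For every student, score = arm × score + c·(1 − arm). This is an exact linear dependence, so the rank is 3 of 4. With pretest added it is 4 of 5, confirmed numerically for c = 0 and c = 50. The terms b2 and b3 cannot be separated.
- *A baseline moderator measured in both arms.* Rank is 4 of 4, or 5 of 5 with pretest, so b3 is estimable.

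The result depends on which students have scores, not on the score values or the sample size.

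**2. What the within-arm slope shows.** Assumptions, none from the documents: a stable ability A; pretest and posttest each loading √r on A, so that their correlation is r; a score correlated λ with A; all variables at unit variance; the same benefit of 0.6 SD for every VR-M student. There is therefore no moderation. Posttest is regressed on score and pretest in n = 60, with 5,000 simulated trials per cell. Percentage of trials with a significant score slope:

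| λ | r = 0.3 | r = 0.5 | r = 0.7 |
|---|---|---|---|
| 0 | 5.5 | 4.7 | 5.2 |
| 0.2 | 8.8 | 8.9 | 8.4 |
| 0.4 | 23.5 | 25.1 | 20.2 |
| 0.6 | 50.4 | 55.1 | 46.2 |
| 0.8 | 80.2 | 88.3 | 85.4 |

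One cell by hand, λ = 0.4 and r = 0.5:

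- Expected slope = λ√r(1 − r)/(1 − λ²r) = 0.1414/0.92 = 0.154.
- Residual variance = (1 − r²) − 0.154² × 0.92 = 0.75 − 0.022 = 0.728.
- Standard error = √(0.728/(57 × 0.92)) = 0.118.
- Ratio = 0.154/0.118 = 1.3, so the chance of exceeding 1.96 is about 25%, matching the table.

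The benefit of 0.6 plays no part: within one arm it only shifts the intercept.

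**3. Power of the estimable alternative.** Posttest on arm, baseline moderator, their product and pretest, at 60:30, with the moderator assumed independent of pretest; 5,000 trials per cell. Interaction is in SD of outcome per SD of moderator.

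| Interaction | r = 0.3 | r = 0.5 | r = 0.7 |
|---|---|---|---|
| 0.2 | 14.5% | 16.8% | 22.1% |
| 0.3 | 26.6% | 32.8% | 43.5% |
| 0.4 | 42.2% | 51.9% | 66.5% |
| 0.6 | 76.2% | 83.2% | 94.2% |

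Mean standard errors are 0.22, 0.20 and 0.167. The interaction needed for 80% power is about 2.8 × SE: 0.62, 0.56 and 0.47.

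**The case against.** No section writes out an arm-by-score term. The aim could be read as asking how response varies among students who received VR-M, a descriptive within-arm question that about 60 students can address. Section 14.0 twice gives examples of moderators and never names the scores, and it cites a textbook on regression-based mediation and moderation. On this reading the fault is one misapplied word in an exploratory clause.

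This stands in part. The interaction is inferred from the role given to moderators, and the sole source is the statement in Exploratory Aim 1. But that statement is unqualified, and lists of examples in Section 14.0 do not withdraw it. If a within-arm predictor was meant, moderator is the wrong name and the correction is the same.

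The false-signal rates also rest on assumption. They run from 5% to 88% with the score-ability correlation, and they adjust only for pretest. Section 14.0 plans the heterogeneity variables as covariates in the outcome models. If three such covariates, each correlated 0.5 with ability (also an assumption), were used here, the rates would fall to 24-32% at λ = 0.6 and 46-67% at λ = 0.8. The size is therefore uncertain. The mechanism remains whenever the score carries ability that the covariates miss.

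Finally, D.4 pairs 2:1 allocation with blocks of four said to give almost equal arms, and a block of four cannot hold an exact 2:1 split. At 45:45, 45 students would lack a score, the ranks would be unchanged, and interaction power would move little (about 72% against 66.5% at 0.4 with r = 0.7).

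**Conclusion.** The concern holds: the plan is wrong as written on this point, and the point is minor. That the scores follow randomisation and exist in one arm only comes directly from Section 4.0, and the failure of the interaction is exact algebra resting on no assumed value. How misleading a within-arm slope would be does rest on assumed correlations and should be taken as illustration. The comparisons for Hypotheses 1 to 6 are not touched, and ASD symptoms, depressive symptoms and cognition remain usable as moderators.

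**What to change.** In Exploratory Aim 1, remove VR-M performance scores from the moderators and list them as a process or dose measure, described within the VR-M arm with no claim of differential effect.

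In Section 14.0:

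- Restrict moderators to baseline variables collected in both arms: SRS-2, the baseline mood survey and the NIH Toolbox.
- State that each is tested by an arm-by-baseline interaction in all randomised students, reported as an estimate with a 95% confidence interval and labelled hypothesis-generating.
- Keep the planned comparison of students with and without poor outcomes, described as showing who does poorly, not who benefits from VR-M.

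If the sponsor wants a causal statement involving the scores, it would need a principal-stratification type of analysis with its assumptions stated.

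The data are unchanged and the cost is wording, with two downsides. One exploratory claim becomes descriptive. The interaction tests have low power, so with three or more moderators and no multiplicity control, a null result is not evidence that moderation is absent; the text should say so.

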Inclusion and exclusion criteria is subject to PI discretion. Some students may still be enrolled after discussion with the teacher if it is determined that they still might be able to participate despite matching exclusion criteria, or not meeting all of the inclusion criteria. These cases will be documented in REDCap. We will also report to IRB as ORIO.

The *inclusion criteria for teachers/educational professionals* are as follows:

- 1. 18 years or older;
- 2. Provides transitional services to students at the participating educational partners: Ann Arbor Academy, Beaumont Hospital, Troy Project Search Program, Southfield Public Schools, and Lincoln Park Avenues Mixter Institute for Transition.

4.0 Procedures Involved:

A. Study Settings

This study will collect human subject data from students in these primary locations: Ann Arbor Academy ([name]) Beaumont Hospital, Troy Project Search ([name]), Southfield Public Schools ([name]), Mixter Institute of Transition ([name]), and Autism Model School ([name]). Other locations to be identified at a later point. Personal information about schools or districts that participate will not be shared without their expressed consent. Each study site is the location of an educational partner where high school students or transition age youth with autism or other ED receive vocational services or a community program serving transition age youth with ED. Each location has classrooms where program evaluation will take place. All students will provide written informed consent (if 18-26) or written assent (if 16-17 years old; with parental permission). Students who are 18-26 and whose parents have educational rights will require the parent to sign.

B. Study Design

We will conduct a single-blind randomized controlled trial to evaluate the effectiveness of VR-M by comparing a vocational services-as-usual group to a group actively using the intervention. We will then conduct a 6 month follow up interview with the participants to evaluate their community outcomes.

C. Study Intervention

SIMmersion, LLC designed VR to enhance job interview skills for adults with SMI. The new tool to be used in Phase II was designed for transition-age youth based on feedback from Phase I. The job-related interview learning goals are:

- 1. Are You someone people want to work with?

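### Section 4.0 D.4 pairs a fixed block of four and announced allocations with no stated concealment safeguard, so some upcoming assignments could be inferred by the team that enrols and assesses students

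*Combined protocol and SAP*

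**What the plan says.** D.4 sets a 2:1 allocation (VR-M to control) from tables made in advance, in "computer generated blocks of four". On the carrier it says: "Envelopes or paper containing the randomization by sequential subject entry number will be created and stored". Each is to be "opened when a participant has completed pre-randomization procedures". On disclosure it says: "Family and teachers will be informed by research team if student is active in the Intervention group or the Control group".

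Other sections show who enrols and assesses:

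- Section 8.0 has the research team obtain student consent or assent at Study Visit 1.
- Section 4.0 D.2 has study staff run the reading test, the baseline role-play and the self-report surveys.
- Sections 4.0 D and 7.0 give the first screen of school records to the teachers, who under D.4 are told allocations.
- Section 3.0 says: "Inclusion and exclusion criteria is subject to PI discretion". It allows entry of students who do not meet every criterion, after discussion with the teacher, with such cases documented in REDCap and reported to the IRB.

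Section 4.0 B calls the trial single-blind but does not say who is blinded. The text reviewed, which lacks part of the site list in Section 5.0, does not mention sealed or opaque envelopes, a custodian for the list, varying or withheld block sizes, or a division between staff who know past allocations and staff who enrol.

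**The concern.** The rule on when a slip is opened protects the current student's assignment. It does not protect the next one. With a fixed block and allocations announced as they occur, anyone who keeps count can work out some later assignments. The people placed to keep count include the research team and the teachers, who between them screen, consent, advise on waivers and run the baseline assessments.

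Foreknowledge could affect which student is brought forward next, whether a borderline student is accepted, and how the baseline role-play is conducted. Section 14.0 adjusts for the pretest score, but that cannot remove differences in unmeasured characteristics such as motivation or teacher support. If the pretest itself were affected, the covariate would carry the distortion. Interview skill and the employment hypotheses (Section 1.0, Phases IIa and IIb) are both exposed. The wide discretion over eligibility makes concealment matter more here than in a trial with mechanical entry criteria.

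**Working it through.** **Inputs.** Block size 4 and ratio 2:1 (Section 4.0 D.4); 90 students planned (Section 1.0, Phase II). The plan gives no figure for predictability. Its one checkable statement is the block design: 4 × 2/3 = 2.67 VR-M slots, so no single block of four can be 2:1. D.4 also says "Blocks of four will ensure nearly equal groups", which fits 2:2 rather than 2:1. The composition is therefore unknown, and three cases are needed.

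**Observer.** This person knows the block size, where each block starts, the composition (or the mix of compositions) and all earlier allocations in the block. An assignment is certain when that history leaves only one possible arm. V is VR-M, C is control.

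**Case A, all blocks 2:2.** There are six equally likely orders. Position 4 is always certain. Position 3 is certain when the first two match, probability 2/6 = 1/3. Share certain = (1/3 + 1)/4 = 33.3%.

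**Case B, all blocks 3:1.** The single C is equally likely at positions 1, 2, 3 and 4, which leaves 3, 2, 1 and 1 certain assignments. The mean is 7/4 = 1.75, and 1.75/4 = 43.8%.

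**Case C, a random mix averaging 2:1.** With p the share of 3:1 blocks, 3p + 2(1 − p) = 8/3 gives p = 2/3. Each 2:2 order has probability 1/3 × 1/6 = 1/18, and each 3:1 order 2/3 × 1/4 = 3/18. The observer knows the mix but not the current block's type.

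- CCVV (1/18): positions 3 and 4 are certain, 2 assignments.
- CVCV and VCCV (2/18 together): position 4 is certain, 1 each.
- VVVC (3/18): position 4 is certain, 1.
- Every other order leaves both arms possible throughout.

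The expected number certain per block is (2 + 2 + 3)/18 = 7/18, and 7/18 ÷ 4 = 7/72 = 9.7%.

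**Counts out of 90**

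| Case | Share certain | × 90 | Best guess correct | Always guessing the more frequent arm |
|---|---|---|---|---|
| A (2:2) | 33.3% | 30.0 | 70.8% | 50% |
| B (3:1) | 43.8% | 39.4 | 81.2% | 75% |
| C (mix) | 9.7% | 8.75 | 72.2% | 66.7% |

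The case C best-guess figure is (12 + 12 + 13 + 15)/(18 × 4) = 52/72 over the four positions. Since 90/4 = 22.5, the last block is half filled. Allowing for that gives 22 × 4/3 = 29.3, 22 × 1.75 + 0.25 = 38.75 and 22 × 7/18 = 8.6, so the range of about 9 to 39 is unchanged.

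**What other block designs do.** Fixed blocks that fit 2:1 are not a cure: size 3 gives 44.4% certain, size 6 gives 28.9% and size 9 gives 21.4%. Random block sizes of 3, 6 and 9, with the current size unknown to the observer, gave about 4% certain and 74% guessed correctly in a simulation of 1,500 trials of 90.

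**The case against.** The strongest reply is that D.4 is thinly reported rather than shown to be unsafe. Several parts of that reply stand.

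- **Block type.** Cases A and B both contradict the stated 2:1. The only use of blocks of four that honours 2:1 is a mix, with about 9 certain assignments rather than 30 to 39. This is why the size is given as a range.
- **Order of events.** Prediction before consent requires the earlier slips in the block to be open already. Recruitment runs through schools and training through class periods. If a whole class completes Visits 1 and 2 before any slip is opened, little can be inferred before consent. The protocol does not state the order. Lists kept by site, or entry numbers used up by students who fail the reading test, could also change the count.
- **Who knows.** A reader might infer that the same individuals enrol students and know every past allocation. The documents assign both tasks to the research team but do not identify individuals, and the undefined single-blind label leaves room for some masked staff.
- **Plain paper.** A reader might infer that a paper list exposes all 90 assignments. The sentence says that the envelopes or paper are opened later, which suggests individual closed slips. An open list is not established.
- **Traceability.** Waived criteria are documented and reported, and Section 13.0 has accrual audited for eligibility. This makes discretionary entries visible afterwards but does not conceal the allocation.
- **Role-play rating.** The protocol does not say who rates the recorded role-play, so biased rating is not shown. Its conduct at baseline is by study staff.

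The core point survives. Following D.4 as written, with one fixed block size and announced allocations, makes some assignments inferable, and no stated safeguard prevents it.

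**Conclusion.** The concern holds as a vulnerability in the design, and it should be corrected. About 10%, 33% or 44% of assignments are certain in advance (about 9 to 39 of 90), depending on a block composition that the protocol does not state. These figures assume one study-wide list, an observer with the full history of each block, and slips opened one after another. They are upper bounds if baseline is completed in batches. The documents do not show that any assignment was in fact foreseen, that selection occurred, or how large any bias in the outcomes would be, so no such claim is made. Reconciling 2:1 with blocks of four is a related but separate matter: correcting the ratio alone, for example with fixed blocks of three, would leave this weakness in place.

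**What to change.** For students not yet randomized, amend D.4 as follows:

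- Remove the option of paper in place of envelopes.
- Use randomly varying block sizes that fit the intended ratio, and do not disclose them to recruiting, assessing or teaching staff.
- Have the list generated and held by someone who neither recruits nor assesses students, and name that role.
- Release each assignment only after consent, the eligibility decision and the Visit 1 and 2 assessments are recorded in REDCap, by sequentially numbered sealed opaque envelope or by electronic release.

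Varying blocks and independent custody are both needed. Varying blocks cut certainty but not guessing: the 3/6/9 example leaves 74% guessed correctly, close to the 72% for mixed blocks of four. Custody and timed release prevent reading ahead and stop a known assignment from altering a student's eligibility decision or baseline.

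If enrolment is complete, which the documents do not say, there is nothing to regenerate. In that case report the block composition, the carrier, who held the list and the order of opening, and state the concealment limitation.

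The cost is a wording change, a new list for the remaining students and a short delay before each release, using the REDCap system already in place. One trade-off needs a decision. Section 13.0 gives the biostatistician a role in data checks and analysis, so if that person holds the list, he or she is unmasked to allocation.
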